### **9.3.2 Eligibility Criteria**

No additional eligibility criteria are needed to define the cohort.

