## **7 Rationale and Background**

COVID-19, the disease caused by the novel coronavirus SARS-CoV-2, has become a global pandemic, affecting countries throughout Europe and the world. At the time of writing of this protocol, three vaccines are being administered in Spain (i.e. Comirnaty and COVID-19 vaccine Moderna) and two approved (Astrazeneca-Oxford and Janssen's) after conditional marketing authorisation by EMA (after granting of the EU Commission on 21st December, 6th January, 29th January, and 11th March 2021 respectively). The real-world effectiveness of these vaccines must be evaluated in Spanish population.

This is an observational cohort study, including patient-level real-world evaluation of the effectiveness of the different COVID-19 vaccines administered in Spain (not ecological evaluation). The secondary data included in the Base de datos para la Investigación Farmacoepidemiológica en Atención Primaria (BIFAP; the Spanish Database for Pharmacoepidemiological Research in Primary Care) will be used [65, 67].

New emerging data on covid infections and vaccinations will not be validated since we will be working with the gold-standard data considered today (i.e. lab results registries for covid infection and vaccinations respectively).

BIFAP has been previously validated for research in pharmacoepidemiology, including the estimations of the precision of several clinical outcomes [65] that will be covariates of the current study (such as cardiovascular/digestive/endocrinological outcomes). Also, vaccination recorded in BIFAP's Table of Vaccines has also been validated [66] that will include the linked official covid vaccinations. The algorithm for maximizing the precision and sensitivity will be utilised for the covariates collection.

As receipt of a newly licenced vaccine may be strongly associated with risk status (e.g., health care workers or essential workers), health status (e.g., at high risk for complications), or lifestyle factors (e.g., adherence to recommendations regarding vaccination, hygiene, self-quarantine, social distancing, and/or mask-wearing), confounding is likely the strongest threat to the validity of an observational study [3-9].

We intent to address confusion through study design (e.g., restriction to scheduled people by calendar time, identifying exchangeable comparison groups/moments) and analysis (e.g., statistical adjustment and stratification).

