## **9 Research Methods**

### **9.1 Study Design**

An observational cohort study of people prioritized for covid-19 vaccination will be implemented to allow for the estimation of effect measures on the absolute scale

(incidence difference) (e.g., time point-specific difference) [10] and relative scale (e.g., time point-specific risk ratios, hazard ratios, and vaccine effectiveness measures). The occurrence of covid-19 infection among unvaccinated and vaccinated patients will be compared as defined below.

This study primarily describes an approach to the retrospective collection of data to using BIFAP data (and linked registry by patient's level) after the necessary data have accumulated (real-time; expected every 2 months starting in 21st December 2021).

The choice of an exchangeable comparator group is a key factor in ensuring a valid study design and addressing confounding. In the current protocol, individuals not yet receiving COVID 19 vaccines will be pooled for a random selection among those with matched criteria to the vaccinated individuals. We have discarded to select the following control groups due to the reason explained below:

- Identified at receipt of a different vaccine such as influenza: the period of influenza vaccination (September-December) seems to be fewer circulation covid-19 since fewer incidences were reported. Thus, they may not be comparable
- During a general practitioner visit: will not be as frequent or representative or a normal non-pandemic situation when people are able to visit the health setting without any restriction. Thus, they may not be comparable
- Choosing a fixed time unit (weeks for instance) to create a series of nested cohorts, each starting at each new time unit [20,21]. Similar to the selected option, this one is valid and although more precise it is more complicated to implement. Also, the variance estimation would need to be adjusted accordingly (e.g., by bootstrapping) because individuals are allowed to contribute to multiple study cohorts [22].

The inclusion and exclusion criteria for the study cohort and thus for the selection of comparative groups are described in the following sections.

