## **9.2 Setting**

This study will be conducted in Spain where the 1st COVID-19 vaccine was included in public campaigns after approval by the European Commission from 21st December 2020. The eligibility criteria will change over time according to prioritised vaccination groups as follows in Figure 1:

Due to the potentially changing incidence of COVID-19 over time and prioritised vaccination groups, comparisons within the study periods and prioritised criteria will be established as much as possible.

According to the 1st prioritized groups (see Figure above), the **study period** will begin on the 21st of December 2020. The end of study period will be the last date of data received at the start of the data collection. Since the vaccines start to request the vaccination for young people (for example: Pfizer requested to the FDA to expand use of its Covid-19 vaccine to adolescents ages 12 to 15 on 9th April 2021), no age restriction will be applied for the source population.

No sex restriction will be applied.

In BIFAP, as per quality and quantity criteria for research, and in order to ensure precise anamnesis, only those clinical histories considered up-to-standard are included in pharmacoepidemiological studies.

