### 9.3.1 Exposure Assessment and Time At Risk

Data will be collected from BIFAP database with data from Spain (described in [Data Sources](#)).

**Inclusion criteria** to the Source population: up-to-standard,  $\geq 1$  year baseline information in January 2021 in BIFAP. The last date of filling all the inclusion criteria will be the inclusion date. No restriction to age or sex will be applied.

**Exclusion criteria:** Patients with prevalent COVID vaccinations or infections ever before (i.e. washout period) the inclusion criteria will be excluded.

**Stop date:** the last moment of the following criteria will define the stop date to contribution: covid-19 infection, death, loss to follow-up and end of study period (the last date available in the data source at data collection).

**Exposure assessment:** The 1st vaccination recorded after the inclusion date will be the time zero for patients included in the vaccinated group, as explained in section 'Definition of Time Zero' [9.1.1.4](#).

From the source population, 10 individuals unvaccinated on or before time zero of the vaccinated pair (10:1) will be randomly selected among those with similar birth cohort, sex and region (matched criteria). Patients included in the comparison group, may be vaccinated later during their follow-up period and then contribute to the vaccinated group (from the date of vaccine administration ahead; i.e. time zero for the vaccinated group).

\*Note: All individuals vaccinated during their follow-up contribution will be included in the vaccinated group. While, a random selection of the unvaccinated individuals will be included as unvaccinated group.

The date and type of vaccine administered will be collected from the **Table of Vaccine** from BIFAP data model. In particular, Covid-19 vaccinations will be ascertained from official covid-19 vaccination registries and provided by the regional governments. The coding system is not known yet. The feasibility analysis will include an evaluation of the coding type, whether or not vaccines are recorded according to standardised system or not. We expect that either ATC07 (J07????) or National Code (CNF [Código Nacional de

Farmacia]) specific for pharmaceuticals in Spain is available for all vaccines administered.

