Patterns of routine health care delivery and utilisation may be disrupted during the COVID-19 pandemic as patients and providers forgo or delay routine preventive, elective, or non-emergency care. These disruptions in health care may result in under-

ascertainment of important patient comorbidities in existing health care databases during periods of disruption.

In order to conduct a valid study and address potential confounding, the eligibility criteria of the study will be restricted relative to the approved indications of the vaccines. Therefore, the results of this study may not be generalisable to the general population but to the restricted population.

With the introduction of a new vaccine, there is the potential for rapidly changing herd immunity in the population. This study is not designed to assess overall and indirect effects of vaccination with COVID-19 vaccines.

Comparative analyses may not be possible in every setting if confounding is deemed to be insurmountable. However, descriptive information about vaccine recipients and crude incidence rates may still be informative and meaningful, even without calculation of vaccine effectiveness measures.

The capture of over-the-counter medications, potentially indicative of short-term disease status (e.g., painkillers, cough medicines, and fever reducers) may not be captured reliably.

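### The restriction by priority group and calendar date announced in Sections 7, 9.1 and 9.2 is not carried into the sampling and matching rules of Sections 9.3.1, 9.3.2 and 9.1.1.5

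*Protocol*

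**What the plan says.** Three sections of the protocol present the cohort as restricted.

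- Section 7, on how confounding will be handled by design, gives as examples "restriction to scheduled people by calendar time, identifying exchangeable comparison groups/moments".
- Section 9.1: "An observational cohort study of people prioritized for covid-19 vaccination will be implemented".
- Section 9.2: "The eligibility criteria will change over time according to prioritised vaccination groups", with reference to Figure 1, and then "comparisons within the study periods and prioritised criteria will be established as much as possible".

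The sections an analyst would program from read differently.

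- Section 9.3.1 requires an up-to-standard record and at least one year of baseline information, and excludes prior COVID-19 vaccination or infection. It adds "No restriction to age or sex will be applied". Everyone vaccinated during follow-up enters the vaccinated group. Ten comparators per vaccinee, unvaccinated at that time zero, are drawn at random within birth cohort, sex and region.
- Section 9.1.1.5 gives the same matching factors. Birth year may be widened to two years, and nursing-home residence is added if the information exists.
- Section 9.3.2: "No additional eligibility criteria are needed to define the cohort".

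**The concern.** If the schedule opens vaccination to some people because of a medical condition, then at a given age, region and date being vaccinated marks that condition. A comparator drawn only on age, sex and region usually will not have it. The two are then not exchangeable at time zero, although Section 7 says the design seeks exchangeable groups.

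The conditions concerned are coded in primary care, so they could be used at the sampling stage. This separates the point from job and nursing-home residence, for which Sections 9.7.4.1 and 9.9 already say data are lacking.

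Two things are at stake. The comparison may carry confounding by indication that the protocol's text suggests has been designed out. And the report could describe a restricted cohort that the sampling rules did not produce.

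**Working it through.** **1. Text comparison.**

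| Element | Sections 7, 9.1, 9.2 | Sections 9.3.1, 9.3.2, 9.1.1.5 |
|---|---|---|
| Who is in the cohort | People prioritised or scheduled at that date | All with an adequate record and no prior vaccination or infection |
| Who is a vaccinee | Implied: member of an open group | Anyone vaccinated during follow-up |
| Who is a comparator | Comparable on priority criteria, as far as possible | Same time zero, birth year, sex, region; nursing home if recorded |
| Link to the schedule | Figure 1 | None |

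Programming the right-hand column never uses priority group. That establishes the inconsistency without any figure.

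**2. Where it has consequences.** For a group opened purely by age, matching on date, birth year and region places vaccinee and comparator largely in the same group, so little is lost. For a group opened by condition, no matching factor represents the condition.

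**3. What is left for condition-based groups.**

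- Section 9.3.4 lists many relevant conditions as updated covariates (diabetes, cardiovascular, respiratory, kidney and liver disease, cancer, immunodeficiency) and leaves the list open. Section 8 names Down syndrome and transplantation as prognostic. Neither is listed by name in 9.3.4, though transplantation is partly reachable through the immunosuppression items.
- Section 9.7.3.2 retains covariates by backward stepwise selection (exit at p ≥ 0.1, entry at p < 0.05), separately for each outcome. A condition that determines who is called can therefore be dropped, most easily in a model with few events.
- Section 9.7.4.1 stratifies by calendar month and by several diseases.

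**4. Precision is not the constraint.** Table 1 gives a probability of 1 that the upper 95% limit lies below 1.00. Inputs: N = 7,720,843; risk in the unexposed 0.0006057; RR 0.05, 0.059, 0.296 and 0.331. With a and b the expected cases among n1 exposed and n0 unexposed:

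- SE = √(1/a − 1/n1 + 1/b − 1/n0); probability = Φ(−ln RR / SE − 1.96).
- This reproduces 1.000 in every row at 1:1 and 2:1, and also at the planned 10:1.
- Least favourable case, RR 0.331 at 10:1: n1 = 7,720,843/11 = 701,895; a = 701,895 × 0.0006057 × 0.331 = 140.7; n0 = 7,018,948; b = 4,251.4; SE = 0.0857; 1.1056/0.0857 − 1.96 = 10.9, so the probability is 1.

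On the protocol's own inputs, systematic error matters more than random error.

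**5. How residual non-exchangeability would act (assumption, not from the documents).** Let k be the baseline hazard of vaccinees relative to their comparators that remains after matching and adjustment. Observed HR = true HR × k, and VE = 1 − HR.

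| True VE | k = 0.5 | k = 1 | k = 2 |
|---|---|---|---|
| 95% (HR 0.05) | 97.5% | 95.0% | 90.0% |
| 70.4% (HR 0.296) | 85.2% | 70.4% | 40.8% |
| 66.9% (HR 0.331) | 83.5% | 66.9% | 33.8% |

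The table shows only that the lower the true effectiveness, the more VE moves, and that it can move either way. The protocol gives no value for k.

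**The case against.** The strongest defence is that the restriction exists in Section 9.2. Section 9.1.1.1 points there for the inclusion and exclusion criteria, and 9.3.2 says only that nothing *additional* is needed. Figure 1 could not be read for this check and may hold a usable schedule. This stands to the extent that one cannot say the protocol contains no restriction. It does not remove the gap: 9.3.1 does not refer to the schedule, the matching does not use it, and 9.2 itself commits only as far as possible.

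A second defence is that much else is in place: matching on date, age and region, month and disease strata, updated covariates, and brand-against-brand comparison, which Section 9.1.1.5 offers specifically against confounding by indication. This also stands. A reader might infer that confounding by indication is left entirely to the Cox covariates, or that restriction is the protocol's main tool. Neither is supported: Section 7 lists restriction as one example among several.

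Third, limiting comparators to people already called has its own risk. Those eligible but unvaccinated may differ in health-seeking behaviour, a bias Section 9.9 recognises. This is a fair cost and shapes the fix.

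Finally, a reader might take "the eligibility criteria of the study will be restricted relative to the approved indications of the vaccines" in Section 9.9 as claiming the same priority-group restriction. It does not: it concerns approved indications, and 9.3.1 does narrow the population through record quality, baseline history and prior infection.

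**Conclusion.** The inconsistency is real. Sections 7, 9.1 and 9.2 announce a restriction by priority group and calendar time that the sampling and matching rules do not carry out. Its practical effect is confined mainly to vaccinees called because of a coded condition; how many there are depends on the Figure 1 schedule. For them, control rests on strata and on covariates that stepwise selection may remove.

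The size and direction of the residual bias cannot be derived from the documents. Section 9.9 itself describes mechanisms that would lower the estimate and others that would raise it. The concern is greatest for hospitalisation and death, where the conditions are prognostic. A reader might infer that every early-campaign estimate is biased, or that VE is understated by a particular amount. The documents support neither: the inputs needed are not given, and any calculation before adjustment ignores covariates the protocol plans to use.

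**What to change.** 1. In Sections 9.3.1 and 9.3.2, refer explicitly to the Section 9.2 / Figure 1 schedule.
2. Derive priority group at time zero from birth year and coded condition, by region and date, for both vaccinees and candidate comparators. Add it to the matching factors in 9.1.1.5 and 9.3.1.
3. At the least, force the priority-defining conditions into the Cox models regardless of stepwise selection, and list them by name in 9.3.4.
4. Report separately those vaccinees whose group cannot be identified from age or coded condition.
5. Keep the present matching as a sensitivity analysis, because comparators who are eligible but unvaccinated may differ in health-seeking behaviour.

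Cost: birth year, coded conditions, region and date are already to be collected. The added work is a table of group opening dates by region and one derived variable. Small groups will have fewer comparators per vaccinee, and some vaccinees will be reported apart from the main estimate. Forcing the conditions into the model alone costs almost nothing.

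If none of this is adopted, amend the restriction statements in Sections 7, 9.1 and 9.2 to describe what is done. The generalisability statement in 9.9 need not be removed, only aligned with the criteria finally used.

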### **9.3.3 Outcome Assessment**

Outcomes will be assessed during the follow-up period (Section 9.3.1). Multiple effectiveness outcomes associated with vaccination for COVID-19 are proposed in this protocol, as the severity of COVID-19 and its complications may vary widely. The severity of COVID 19 illness has been shown to vary from asymptomatic to life-threatening.

#### **9.3.3.1 Laboratory-confirmed COVID-19**

As Main outcome: cases will be incident **laboratory-confirmed covid-19** infections recorded in a covid-19 registry (regardless the symptoms, severity or the result of the COVID infection). Infection may be confirmed through positive PCR, Antigens or any other confirmatory criteria established by clinical protocols (that definition is out of the scope of the current study). That registry will be linked with BIFAP's primary care electronic health records (PC eHR). The date of the COVID cases will be the 1st date the sample was taken for testing as recorded in the lab registries linked to PC eHR.

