**Variables:**

- COVID-19 vaccinations will be identified from a vaccination registry linked with each patient's primary care clinical history.
- Medically attended diagnosis of COVID-19 in any setting will be identified through linked registries of 1) COVID positive test results, 2) hospital COVID diagnosis or discharged COVID diagnosis.
- Covariates will be collected from primary care eHR. Covariates will include demographic information, morbidities, medication use, health care utilisation, markers of current disease status at time zero, and markers of frailty.

**Data sources:** Base de datos para la Investigacion farmacoepidemiológica en Atención Primaria (BIFAP) and linked registries of 1) COVID positive test results, 2) hospital COVID diagnosis or 3) discharged COVID diagnosis

**Study size:** BIFAP database includes up-to-standard information for around 7.7 million patients aged  $\geq 18$  years.

**Data analysis:** Characteristics of the vaccinated and unvaccinated groups at baseline will be described. Incidence rates of COVID-19 outcomes will be calculated and compared between the two groups, and vaccine effectiveness measures will be estimated by 1 minus the hazard ratios (HR; 95%CI). Additional time period-specific effect estimates (e.g., at 3, 6, or >6 months after vaccination) will also be estimated.

Stratified analysis will separately estimate vaccine effectiveness in clinically meaningful subgroups and calendar periods. Sensitivity analyses will evaluate the robustness of the study approach across variations of the study methodology.

**Milestones:** Evaluation of the availability of data will start during 1-15 June but timelines may be impacted by the date the data are received from the different regions and BIFAP common data model is ready for evaluation (End of July).

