## **8 Research Question and Objectives**

This study addresses the research question of whether vaccinations with new licenced COVID-19 vaccines, (Comirnaty, Moderna, AstraZeneca's and Janssen and subsequently

approved vaccines in the EU during the data collection), are effective in reducing the burden of COVID-19 in Spain in comparison with no vaccination periods.

**Primary objective** is to evaluate the effectiveness of each COVID-19 vaccine in reducing the covid-19 infections (confirmed through test and regardless the prognosis and clinical phenotype (i.e. whether symptomatic or asymptomatic, mild or severe).

**Secondary objectives** of this study will be splitting the effectiveness

- by the following outcomes:
  - asymptomatic (defined as a positive test (whether PCR or antigens) without recorded symptoms in primary care +/-14days of the date the sample was taken). Note: In epidemiological vigilance protocols, among asymptomatic patients, isolation must be maintained till 10 days after the date when the sample was taken.
  - symptomatic (defined as positive test (whether PCR or antigens) with recorded symptoms in primary care or Hospitalisations/Intensive care unit (ICU) admissions +/-14days of the date the sample was taken (or at anytime linked with the test result))
  - Hospitalisations/Intensive care unit (ICU) admissions for COVID-19 at anytime linked with the test result or within +/-14days of the date the sample was taken (if hospitalisation was recorded in primary care clinical profile)
  - All-cause mortality as a recorded death with COVID 19 listed as an underlying cause of death on cause-of-death registers, or a death during a hospitalisation, with COVID-19 as a listed diagnosis, or a death within a specified time period (e.g., 28 days) after a diagnosis or hospitalisation for COVID 19.
- over clinically meaningful subgroups (old people; patients with cardiovascular disease, diabetes, or chronic pulmonary disease, chronic renal impairment, treated cancer, patients with a history of transplantation, Down Syndrome found linked with the prognostic of the covid-19 infection; as well as smoking, males and obesity suspected linked with the prognosis in some studies)
- along the time since complete vaccination (up-to 3 months, 6 months and ever after).

A feasibility evaluation will be conducted before the start of the study to evaluate the availability of key data elements and the appropriateness of the study design.

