#### **COVID-19 Test results (PCR, antigens, etc.)**

Test results for coronavirus will be linked with PC eHR. For effectiveness analysis, cases will be positive covid infections recorded in that registry that may be confirmed through positive PCR, Antigens or any other confirmatory criteria established by clinical protocols (that definition is out of the scope of the current study).

Laboratory-confirmed infection is considered gold-standard to identify cases for the main analysis, thus no predictive values will be estimated. As explained below, identification of so-called 'possible' covid cases recorded only through diagnosis coding (without lab information) will be performed in a Sensitivity analysis (Section 9.7.4.2).

Also, an estimation of the concordance between the observed incidences in BIFAP and those 'expected' will be performed (i.e. external validation) as a proxy for the accurateness to identify cases in BIFAP and discussion of potential reasons if differences would be present.

The 'expected' cumulative incidences will be calculated by dividing the COVID cases reported daily to RENAVE (base de datos de vigilancia epidemiológica; by calendar period, region and age) by the population reported in the Spanish National Statistics Institute for that year [73]. Access to RENAVE will be available by one of the institution collaborating in the current study [74].

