#### **9.3.3.2 Symptomatic or Asymptomatic Diagnosis of COVID-19**

In a secondary analysis, in order to inform about the effectiveness to protect against asymptomatic and symptomatic infections, outcomes from the main analysis will be divided according to the symptoms recorded around the date of confirmed covid-19 in the patient PC eHR. Two effectiveness parameter, i.e. to protect against asymptomatic and asymptomatic infection, will be estimated separately for each vaccine. The date of the COVID cases will be the 1st date the sample was taken for testing.

Cases of **Asymptomatic** infection will be defined as a positive test without recorded symptoms in primary care  $\pm$ 14days, hospitalisations/Intensive care unit (ICU) or hospital diagnosis of the date the sample was taken). In asymptomatic analysis, symptomatic infections will participate as non-cases stopping at covid date.

Cases of **Symptomatic** infection will be defined as a positive test with recorded symptoms in primary care  $\pm$ 14days of the date the sample was taken, or linked Hospitalisations/Intensive care unit (ICU) admissions. In symptomatic analysis, asymptomatic infections will participate as non-cases stopping at covid date.

Note: In epidemiological vigilance protocols, among asymptomatic patients, isolation must be maintained till 10 days after the date when the sample was taken. For a sensitive approach we will broaden till 14 days in order to allow for delayed records in PC eHR.

\*Note: some misclassification may be present since patients with mild disease (mild symptoms) may never seek care that will be assumed as asymptomatic.

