The validity of coding for future COVID-19 vaccines—including the ability to distinguish between separate products—or COVID-19 outcomes is unknown at this time, and the likelihood of missing data on specific vaccine brand may be high. Misclassification of vaccine exposure, outcome status, or covariates is possible in existing health care data not collected for research purposes. Information about COVID-19 infection (through test results or codes) may not be captured reliably in databases. Additionally, COVID-19 testing is not systematic, and laboratory confirmation of case status may not be available for many patients. Currently, bias may be minimised since COVID 19 testing becomes near universal and repeated with individuals, with similar testing capacity and practice across regions, though. Since we will not have any better gold-standard for case status than the information about confirmed covid-19 infection through lab results (used for case definition in the current study) its precision will not be evaluated but with the expected external incidences published by the Health authorities.

Also, we consider that if COVID misclassification occurred it would be similar in both, vaccinated and unvaccinated groups, however surveillance or detection bias (different likelihood of screening or testing for COVID between the groups) cannot be discarded. If vaccinated individuals had less likelihood of screening or test than unvaccinated, we would artificially observe more cases among unvaccinated, directing toward a biased higher vaccine effectiveness estimation.

Data from multiple regions and sources will be merged in BIFAP and included in the study, thus, there may be variation in the capture and recording of various clinical elements. Additionally, different types of data sources will be used (e.g., records from general practice and lab results from other registers) as well as different coding systems, then variables defined in different data sources may not exactly represent the same concept across data sources. Thus, heterogeneity of vaccine effectiveness estimates across data sources may be due to the underlying heterogeneity of confounding control, misclassification, or other data source factors rather than true differences in vaccine effectiveness.

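### The primary case rule leaves its confirmatory tests open, and is wider than the PCR-or-antigen rule for the symptomatic and asymptomatic outcomes said to be a split of it

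*Protocol*

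**What the plan says.** **Primary outcome.** Section 9.3.3.1 takes incident laboratory-confirmed infections from a COVID-19 registry and states: "Infection may be confirmed through positive PCR, Antigens or any other confirmatory criteria established by clinical protocols". On what those other criteria are, it adds that "that definition is out of the scope of the current study". Section 9.1.1.2 (COVID-19 Test results) gives the same rule: "confirmed through positive PCR, Antigens or any other confirmatory criteria established by clinical protocols".

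**Secondary outcomes by symptoms.** Section 8 names the tests. One outcome is "asymptomatic (defined as a positive test (whether PCR or antigens) without recorded symptoms in primary care"; the other is "symptomatic (defined as positive test (whether PCR or antigens) with recorded symptoms in primary care". The Abstract has the same limit. Section 9.3.3.2 requires only a positive test, without naming the type, and says that "outcomes from the main analysis will be divided according to the symptoms recorded around the date of confirmed covid-19".

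**Sources.** The Abstract's Variables paragraph says: "Medically attended diagnosis of COVID-19 in any setting will be identified through linked registries of 1) COVID positive test results, 2) hospital COVID diagnosis". Section 9.1.1.2, however, sends cases known only from a diagnosis code, with no laboratory information, to the sensitivity analysis in 9.7.4.2.

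**Misclassification.** Section 9.1.1.2 treats the laboratory result as the gold standard and estimates no predictive values. Section 9.7.4.3 plans no quantitative bias analysis. Section 9.9 takes the view that "if COVID misclassification occurred it would be similar in both, vaccinated and unvaccinated groups", conceding only that detection may differ between groups.

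**The concern.** The case definition of a primary outcome belongs in the protocol. Here it is not deferred to an analysis plan. It is handed to clinical protocols that are neither named nor versioned, so the set of accepted tests is unknown and could differ by region or change during follow-up.

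The quantity wanted is new infection. PCR and antigen tests look for the virus. A test of immune response does not: depending on the assay, vaccination can turn it positive, and so can an infection long past. The washout in 9.3.1 can remove only earlier infections that were recorded. An old, unrecorded infection found by such a test would be dated at its sample and counted as incident.

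False cases caused by the vaccine can arise only after vaccination, so they add to one side of the comparison. At the effectiveness the plan expects for the mRNA vaccines there are few true cases among the vaccinated, and a small number of false ones would move the estimate.

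**Working it through.** **1. Trace one record through the definitions.** Take a registry case confirmed only by a criterion other than PCR or antigen.

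| Place | Tests accepted | Is this record a case? |
|---|---|---|
| 9.1.1.2 and 9.3.3.1, primary | PCR, antigen, other criteria | Yes |
| 9.3.3.2, symptomatic or asymptomatic | positive test, type not stated | Yes, in one of the two, if the other criterion is a test |
| Section 8 and Abstract, symptomatic or asymptomatic | PCR or antigen | No, in neither |

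Within 9.3.3 the two parts can add up to the primary outcome. Under the Section 8 wording they do not. Two programmers could build different outcomes from the same Protocol.

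**2. Would a planned analysis show an excess of false cases among the vaccinated?**

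- The comparison with national surveillance incidence (9.1.1.2, 9.7.4.3) is by region, calendar date and age, not by vaccination status.
- The sensitivity analysis in 9.7.4.2 widens the case definition by adding code-only cases. None narrows it to PCR or antigen.
- No predictive values are estimated for the main definition, and no bias analysis is planned.

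So none would.

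**3. The plan's own figure.** Table 1 (section 9.5) gives probability 1 that the upper 95% limit of the risk ratio (RR) is below 1.00. Inputs: N = 7,720,843; unexposed risk p0 = 0.0006057; RR = 0.05, 0.059, 0.296 and 0.331 (Pfizer/BioNTech, Moderna, AstraZeneca, Janssen). For Pfizer/BioNTech at 1:1:

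- unexposed cases = 3,860,421.5 × 0.0006057 = 2,338
- exposed cases = 2,338 × 0.05 = 117
- SE of log RR = √(1/117 + 1/2,338) ≈ 0.095
- −ln(0.05)/0.095 ≈ 31.5, far above 1.96, so the probability is 1

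All eight rows reproduce as 1. That figure is not in dispute. It also gives no protection here: with 6.057 false cases per 100,000 vaccinees (10% of p0) the probability at 1:1 is still 1 for every brand, although the VE estimate has moved by 10 points.

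**4. Illustration of the bias.** Let f be the number of false cases per 100,000 vaccinees per 14 days, in the vaccinated only. The Protocol gives no value for f, so the values below are assumptions.

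Observed VE = 1 − (RR + f/60.57)

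Loss per unit of f = 1/60.57 = 0.0165, or about 1.65 VE points for every brand.

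| Brand (planned VE) | f = 0 | f = 1 | f = 2 | f = 5 |
|---|---|---|---|---|
| Pfizer/BioNTech (95%) | 95.0 | 93.3 | 91.7 | 86.7 |
| Moderna (94.1%) | 94.1 | 92.4 | 90.8 | 85.8 |
| AstraZeneca (70.4%) | 70.4 | 68.7 | 67.1 | 62.1 |
| Janssen (66.9%) | 66.9 | 65.2 | 63.6 | 58.6 |

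For scale, true cases at 95% VE are 60.57 × 0.05 = 3.03 per 100,000 vaccinees per 14 days.

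**5. How far the illustration depends on its assumptions.**

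- *False cases in both groups* (old infections). Observed RR = (RR × 60.57 + f1)/(60.57 + f0), with f1 in the vaccinated and f0 in the unvaccinated. With f1 = f0 = 5 and RR = 0.05: (3.03 + 5)/65.57 = 0.122, so VE is 87.8% rather than 86.7%.
- *Direction.* The observed RR falls below the true RR only if f1 < RR × f0. VE would then be too high.
- *Baseline.* The 60.57 counts symptomatic cases (section 9.5), while the primary outcome counts infections whatever the symptoms. With a baseline twice as large, assumed for illustration, the loss per false case is 1/121.14, or about 0.83 points.

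**The case against.** The strongest objection is that the Protocol never mentions antibody tests. It asks for confirmed, incident infection, and the other criteria are those that clinical protocols accept as confirming it. Nothing shows that those protocols accept serology, or that the registry records it. This stands. A reader might infer that antibody positives would be counted as breakthrough infections and that the primary VE is biased downward. The documents do not support that: they show only that the rule does not exclude such results.

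Three further objections have weight.

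- The direction is not fixed in every case. False cases from old infection can occur among the unvaccinated too (step 5). The downward direction is certain only for positives caused by the vaccine.
- The hospital-diagnosis wording in the Abstract is a smaller matter than it looks. The Abstract's objective already requires confirmation by test, code-only cases already go to sensitivity analysis, and the hospital source is needed for the hospitalisation outcome.
- A registry study may reasonably follow the official case definition, with test-type codes left to an analysis plan or code list. That would answer a gap. Here the Protocol states a rule, declares its content out of scope, and gives a narrower rule elsewhere for what it calls parts of the same outcome.

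The feasibility stage and the external comparison of incidence are real checks on data validity, but neither is split by vaccination status.

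**Conclusion.** The point holds as a defect of definition. The primary outcome accepts unspecified confirmatory criteria and is wider than the PCR-or-antigen definition in Section 8 and the Abstract, although 9.3.3.2 presents the symptomatic and asymptomatic outcomes as a division of the primary cases. That contradiction rests on the text alone.

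The bias is conditional. If the other criteria include a test of immune response, positives due to vaccination or old infection could enter as incident cases. Those due to vaccination would lower VE, contrary to the view in 9.9 that misclassification would be similar in both groups, and no planned analysis would detect it. The size cannot be derived from the documents and is zero if the registry holds no such results. The figure of about 1.65 VE points per false case per 100,000 vaccinees per 14 days assumes false cases among the vaccinated only and the symptomatic baseline of 60.57. It is a scale for judging the risk, not an estimate of it.

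**What to change.** - In 9.1.1.2 and 9.3.3.1, define the primary case as the first positive PCR or antigen test, dated at that sample. This matches Section 8.
- Analyse registry cases confirmed only by other criteria in the 9.7.4.2 sensitivity analysis, alongside the code-only cases already placed there.
- Use the same test wording in the Abstract, Section 8 and 9.3.3.2, so that the symptomatic and asymptomatic outcomes are a true split of the primary cases.
- In the Abstract's Variables paragraph, make clear that a hospital diagnosis without a positive test is not a primary case. The body of the Protocol already says so, and only this wording needs to follow.

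The cost is protocol wording and a filter on test type at extraction. A few genuine cases confirmed by other means would move from the main to the sensitivity analysis. If the registry holds only PCR and antigen results, the filter removes nothing. The Table 1 probabilities stay at 1.
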